8 STATISTICAL METHODS

8.1 General Statistical Conventions

All statistical procedures will be completed using SAS Grid version 9.4 or higher.

Unscheduled visit results will be included in date/time chronological order, within subject listings only. Unscheduled visit shall not be summarized in tables.

Categorical variables will be summarized using number (n) and percentage in each category including missing category if any. All percentages will be rounded to one digit after decimal point. The number and percentage will be presented in the form XX (XX.X %), where the percentage is in the parentheses. If the percentage of a category is "100", then display it as "100" (do not add decimal after 100). 95% confidence intervals will be presented along with frequency counts and percentages for primary and secondary safety endpoints.

Continuous variables will be summarized using number of subjects (n), number of missing subjects, mean, median, standard deviation (SD), minimum, and maximum for continuous variables. All mean and median values will be formatted to one more decimal place than the measured value. Standard deviation values will be formatted to two more decimal places than the measured value. The minimum and maximum will be displayed to the same number of decimal places as the original data. For pharmacokinetic data, geometric mean (with one decimal than the measured value) and geometric CV % (with 1 decimal place) will be presented

additionally.

All general summaries will be presented by Overall, having all the subjects, unless otherwise specified. For safety assessments, the summaries will be presented by titration and maintenance combined, follow-up and overall, unless otherwise specified.

All subject data will be presented in individual subject data listings. All listings will be sorted for presentation in order of dose level if applicable, subject number (including site ID), date/time and visit. The dose level as well as subject's sex, age and race will be stated on each listing. In general, no imputed dates or values will be presented in listings unless specified.

8.2 **Subject Disposition**

The following categories will be summarized only for "Overall" Column. The summary is based on all subjects.

- No. of subjects screened
- No. of subjects who screen failed
- No. of subjects who re-screened
- No. of subjects who complete visit 3 during baseline period (Enrolled Population)
- No. of baseline failure subjects
- No. of subjects who completed the baseline period

The following categories will be summarized overall. The summary is based on Enrolled population.

- No. of subjects who completed study
- No. of subjects who discontinued from study
- Primary reason for study discontinuation
- No. of subjects who completed treatment
- No. of subjects who discontinued from treatment
- Primary reason for treatment discontinuation
- No. of subjects who entered titration period
- No. of subjects who completed treatment during titration period
- No. of subjects who discontinued treatment during titration period
- No. of subjects who entered maintenance period
- No. of subjects who completed treatment during maintenance period

• No. of subjects who discontinued treatment during maintenance period

In addition, number of subjects in the safety population who completed or discontinued during titration and maintenance period will be summarized by last dose level assigned during the specified period.

A listing of subject disposition will be provided for all subjects, with the extent of their participation in the study and the reason for discontinuation from study or treatment.

Additionally, a listing of inclusion/exclusion criteria will be presented for all subjects.

8.3 **Protocol Deviations**

A summary of subjects excluded from safety population, efficacy population, pharmacokinetic and pharmacodynamic populations will be presented by enrolled population.

A summary of major (key) protocol deviations will be presented for Enrolled population. All protocol deviations will be listed.

8.4 **Demographics and Baseline Characteristics**

Subject characteristics and demographics will be summarized for the Enrolled population. The summary will include descriptive statistics such as the number of subjects (n), mean, SD, median, minimum (min), and maximum (max) for continuous measures and frequency counts and percentages for categorical measures. No formal statistical comparisons will be made among dose levels.

The following demographics will be summarized: Age (years), Height (cm), Weight (kg), Body Mass Index (BMI) (kg/m²), Systolic Blood Pressure (mmHg), Diastolic Blood Pressure (mmHg), Sex, Child bearing potential for female population, Race (Primary, Secondary and subcategory) and Ethnicity.

Baseline disease characteristics include:

- Baseline eGFR
- Baseline AST or ALT levels
- Baseline Total Bilirubin levels
- History of ADPKD

Above summary of demographics and baseline characteristics will be repeated for safety and efficacy populations if any subject in the Enrolled population was excluded from these two populations.

A listing including demographic and baseline characteristics will be presented separately by subject for all subjects.

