Baseline Period (Visits 3 - 5): Following completion of all Screening assessments and establishment of background medication stability, subjects will enter the 3-week no study drug treatment Baseline Period during which time liver chemistry tests and serum creatinine (for eGFR determinations) will be assessed weekly to establish a baseline and assess individual variability. Baseline trough spot urine specific gravity (as a point-of-care surrogate for urine osmolality) and U_{osm} will be determined only at Visit 5. Visits 3 and 4 may be conducted remotely by a HHC. At the successful completion of the Baseline Period (Visit 5), subjects will be dispensed study drug and begin treatment. This completes the Baseline Period and subjects will enter the Titration Period.

Titration Period (Visits 6 - 11): During a period of 3-6 weeks, the lixivaptan dose will be increased weekly according to the titration schedule (Table 4) to achieve a level that results in both a tolerable dose and reduced first morning (trough) spot urine specific gravity (as a point-of-care surrogate for urine osmolality) or until the maximum dose level (Level 4 [200 mg BID]) is reached. Dosing will be started at Level 1 (50 mg BID), but the minimum dose to enter the Lixivaptan Maintenance Period is Level 2 (100 mg BID). In most circumstances, dose tolerability will be confirmed during an additional week of dosing before the subject advances to the Maintenance Period. At the 2 highest dose levels (Level 3 and Level 4) where aquaretic effects may be problematic in certain subjects, there will be an opportunity to reduce the evening (PM) dose (Level 3a [150 mg AM/100 mg PM] and Level 4a [200 mg AM/150 mg PM]; see Section 5.2). Liver chemistry tests will be assessed weekly during the Titration Period. Urine specific gravity and U_{osm} will be measured at all titration visits that occur except Visit 11. All titration visits may be conducted remotely by a HHC with telemedicine.

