Maintenance Period (Visits 12 - 24): Subjects will continue to receive lixivaptan at the dose achieved at the end of the Titration Period for up to 52 weeks (12 months). The investigator will have the ability to lower the dose if necessary, to improve tolerability. Assessments, including liver chemistry tests, will be performed every 4 weeks during this period. Visits 12, 13, 14, 15, 16, 18, 19, 20, 21, 22, and 23 may be conducted remotely by a HHC. If conducted remotely, Visits 14 and 20 will include telemedicine and the other visits may include telemedicine if deemed necessary by the Investigator.

Follow-up Period (Visits 25 - 27): After the last dose of lixivaptan is given, the subjects will enter the Follow-up Period which will last 4 weeks. Three assessments of serum creatinine to determine eGFR will be obtained starting as early as the 8th day after the final dose of study medication and continuing through the 28th day of the Follow-up Period. Visits 25 and 26 may be conducted remotely by a HHC (using telemedicine if deemed necessary by the Investigator). Other routine safety assessments will be performed at the last visit (Visit 27).

Study assessments including clinical laboratory tests, spot urine collections, physical examination findings, vital signs, ECGs, trough PK sampling, and monitoring of AEs will be performed at the timepoints presented in the Schedule of Procedures (Table 1). Serious AEs (SAEs) will be recorded from the time the subject signs the Informed Consent Form (ICF) until exit from the study. All other AEs will be recorded from the start of the Titration Period until exit from the study.

The maximum study duration is 73 weeks (16.8 months). Note that the study may be interrupted at any time if safety issues compromise the safety of the subjects.

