 - Complete Chemistry Panel will be obtained at V1, V5, V11/Last Titration, V14, V17, V20, V24/ET, V27. If a subject required adjustment of blood pressure medications during Screening, then a repeat Complete Chemistry Panel will be performed at V2.
 - Liver Chemistry Panel will be obtained at V1, V3-V24/ET, and V27. If a subject requires adjustment of blood pressure medications during Screening, then a repeat Liver Chemistry Panel will be performed at V2.
 - Serum creatinine will be obtained at V3, V4, V25 and V26.
 - eGFR will be calculated and reported whenever serum creatinine is obtained either as part of the Complete Chemistry Panel or when serum creatinine alone is measured.
 - Hepatitis B surface antigen (HBsAg) and hepatitis C virus antibody (Anti-HCV) will be obtained at V1 only.

h Hematology blood samples will be obtained at V1, V5, V11/Last Titration, V17, V24/ET, and V27.

i First morning, fasting urine specific gravity and osmolality (AM trough) will be obtained at V5, at every visit during the Lixivaptan Titration Period (except V11/Last Titration) and at V24 and V27. Dispense container and review instructions (including not to take study drug on the morning of the next visit) with subject at V4-V9, V23, and V26.

Version: Final 1.0, Date: 01 Dec 2020 Page 19 of 42

- j Trough (7-10 AM prior to AM dose) plasma specimens for measurement of lixivaptan will be obtained at V5, at the final visit during the Titration Period (V11/Last Titration), and during the Maintenance Period *if* ALT levels >3 x ULN and/or total bilirubin >2 x ULN occur.
- k Utilizing a separate informed consent, all subjects will be asked to provide a DNA sample at the end of the Baseline Period (V5) to assess genetic variants associated with hepatic abnormalities (if and when feasible).

1 Serious adverse events (SAEs) will be collected throughout the study beginning with signing of informed consent. All non-serious adverse events will be collected beginning at the start of the Titration Period. Adverse Events of Special Interest (AESI) include hepatic events and pregnancy and will be reported on special forms using the SAE pathway of reporting.

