8.6.2 Analysis of Secondary Safety Endpoint

Similarly, descriptive statistics (n and percentage) along with exact binomial 95% CI will be presented to summarize the following 2 secondary endpoints:

- The proportion of subjects who develop ALT levels >5 x ULN that were assessed by the independent HERC to be related to lixivaptan and resulted in discontinuation of the study drug during the Titration and Maintenance Periods.
- The proportion of subjects who develop ALT levels >3 x ULN that were assessed by the independent HERC to be related to lixivaptan and resulted in dose reduction of the study drug during the Titration and Maintenance Periods.

The above summaries will be presented additionally based on the investigator decision alone as documented in the CRF.

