8.6.3 Analysis of Additional Hepatic Safety Endpoints

The proportion of subjects along with the exact binomial 95% CI who develop the following abnormalities during the Titration and Maintenance Periods will be tabulated and presented descriptively:

- >3 x, 5 x, >10 x, and 20 x ULN elevations for ALT
- >3 x, 5 x, 10 x, and 20 x ULN elevations for Aspartate aminotransferase (AST)
- >3 x, 5 x, 10 x, and 20 x ULN elevations for either ALT or AST
- ALT or AST levels >2 x their baseline
- Any elevation of total bilirubin (TBL) $>2 \times ULN$
- Any elevation of alkaline phosphatase (ALP) >2 x ULN
- Elevation of aminotransferase (>3 x ULN) accompanied by elevated bilirubin (>2 x ULN) will be evaluated using Drug-Induced Serious Hepatotoxicity (eDISH) plots
- Elevation of aminotransferase in temporal association with nausea, vomiting, anorexia, abdominal pain, or fatigue will be explored graphically using swimmer plots.
- Possible liver-related deaths and liver-related treatment discontinuations.

The liver dysfunction occurring during the titration and maintenance period judged using the Drug Induced Liver Injury Network (DILIN) (Appendix II) probability criteria independently by investigator and HERC will be listed separately.

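### SAP 8.1 bars unscheduled results from all tables with no exception for the hepatic endpoints, so an ALT crossing seen only at an off-schedule test can go uncounted

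*SAP*

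**What the plan says.** SAP 8.1 (General Statistical Conventions) has two sentences on unscheduled data: "Unscheduled visit results will be included in date/time chronological order, within subject listings only", followed by "Unscheduled visit shall not be summarized in tables". Neither carries a qualifier. Two other summary rules in the same section do, for example "For safety assessments, the summaries will be presented by titration and maintenance combined, follow-up and overall, unless otherwise specified".

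The hepatic endpoints are defined by period, not by visit. SAP 4.1 and 4.2.1 count subjects who develop ALT above 3 x or 5 x ULN in Titration or Maintenance. SAP 8.6.2 covers elevations that "resulted in dose reduction of the study drug during the Titration and Maintenance Periods", and SAP 8.6.3 covers subjects "who develop the following abnormalities during the Titration and Maintenance Periods will be tabulated". None of 8.6.1, 8.6.2 or 8.6.3 says whether unscheduled, repeat or local-laboratory values count.

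The schedule is in SAP Table 3 (section 3.3.2), footnote g: "Liver Chemistry Panel will be obtained at V1, V3-V24/ET, and V27". For Maintenance, Protocol 3.1.2 says: "Assessments, including liver chemistry tests, will be performed every 4 weeks during this period". For Titration it says: "Liver chemistry tests will be assessed weekly during the Titration Period".

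Protocol 7.3.7 to 7.3.7.2 add liver tests outside that schedule:
- within 48 hours of suspicious symptoms or signs;
- within 48 hours of a transaminase above 3 x ULN or total bilirubin above 2 x ULN;
- weekly or more often in the first month while values remain raised;
- more often after smaller rises, above all in Maintenance.

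**The concern.** The protocol looks hardest at the liver between scheduled visits, and the SAP's general table rule discards what is found there. A programmer who follows SAP 8.1 as written has authority to drop those values from the endpoint counts.

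Hepatic safety is the primary question, and the error runs one way: leaving out a crossing can only lower a count. Protocol 8.7 allows the SAP to modify the protocol's plans, so the protocol's period-based wording does not clearly prevail over SAP 8.1.

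The issue survives early termination. SAP 9 cuts the outputs, but SAP Appendix IV keeps Table 14.3.2.1, which summarises the primary and secondary hepatic endpoints.

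**Working it through.** The documents give no figure to reproduce. The sample size of up to 50 rests on analogy with another study. The check is a reading of the text, with simple arithmetic for scale.

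**1. Is there an exception anywhere?** None was found in SAP 8.1, 8.6.1 to 8.6.3 or 8.6.6. The only other rule on unscheduled visits, in SAP 7.2.2, is a further exclusion, for eGFR.

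**2. What does the 8.1 rule add?** The by-visit summaries of laboratory data (8.6.6), vital signs (8.6.7), ECG (8.6.9) and trough concentrations (8.7.2.1) are already tied to scheduled time points in their own sections. For those displays 8.1 adds little. Its separate effect falls on results not tied to a visit, such as the hepatic counts.

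**3. How far apart are scheduled panels?**
- Maintenance: V12 to V24 gives 24 - 12 + 1 = 13 panels, and 13 x 28 = 364 days.
- Longest Maintenance gap with the +/-3-day window: 28 + 3 = 31 days if the window runs from the prior visit, or 28 + 6 = 34 days on a fixed calendar.
- Longest Titration gap: 7 + 3 = 10 days or 7 + 6 = 13 days on the same two assumptions. The risk there is much smaller.

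**4. Which outputs are exposed?**

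| Output | How a case could be lost | Exposure |
|---|---|---|
| Primary: >3 x ULN with discontinuation | First seen off schedule, with no later scheduled or early-termination (ET) value above 3 x ULN in the period | Lower |
| Secondary: >5 x ULN with discontinuation | Peak reached only at a retest | Higher |
| Secondary: >3 x ULN with dose reduction | Subject stays on drug, so the event triggers no ET panel; ALT may fall before the next scheduled panel | Higher |
| 8.6.3 threshold tiers and eDISH plots | Any crossing seen only off schedule | Exposed as planned; not produced after termination |

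**5. What is one omitted subject worth?** SAP 8.6.1 names the exact binomial interval. The Clopper-Pearson limits for x events in n subjects are the 2.5% quantile of Beta(x, n - x + 1) and the 97.5% quantile of Beta(x + 1, n - x). The lower limit is 0 when x = 0.

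| n | Case omitted | Case counted |
|---|---|---|
| 50 (planned maximum) | 0/50 = 0%, CI 0 to 7.11% | 1/50 = 2.0%, CI 0.05 to 10.65% |
| 6 (assumed) | 0/6 = 0%, CI 0 to 45.93% | 1/6 = 16.7%, CI 0.42 to 64.12% |

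For the terminated study, SAP 9 gives only the 6 subjects who entered Maintenance. The Safety Population size N is not stated but is at least 6. One subject is therefore worth 100/N points, at most 100/6 = 16.7.

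**The case against.** The best case against this is that 8.1 is only a display convention.

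- **SAP 7.2.2** separately bars unscheduled values from the eGFR calculation. That would be largely redundant if 8.1 already kept them out of every tabulated result.
- **SAP 8.6.4** tabulates the Appendix III hepatic tests, which are done on request after an abnormality and have no row in the visit schedule. Literal use of 8.1 would leave that table largely empty.
- **Endpoint definitions** are period-based, and a specific definition ordinarily governs a general convention.
- **Adjudication:** all elevations above the 3 x ULN transaminase threshold go to the Hepatic Events Review Committee (HERC), and its eCRF feeds the primary and secondary endpoints (Protocol 7.3.7.2, 7.3.7.3 and 7.3.10).
- **AESI reporting:** any ALT or AST above 3 x ULN is reported as an adverse event of special interest, and Appendix IV keeps the AESI table (14.3.1.2.4).
- **Scale:** the study ended early, and a reader can check each case in Listings 16.2.7.2 and 16.2.8.1.3.

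Much of this stands. A by-visit intent is plausible, the primary endpoint is fairly well protected, and no value disappears from the record. But nothing cited says that 8.1 yields. SAP 8.6.4 shows 8.1 in conflict with the SAP's own tables, which is a further reason to correct it. The documents do not say that the HERC eCRF records the ULN multiple, or which source governs the ALT criterion. The AESI table does not show the 5 x ULN tier. SAP 8.6.1 and 8.6.2 also require summaries on the investigator's decision alone, which adjudication does not protect. The ET visit is only encouraged (Protocol 4.2.3). Listings let a reader spot an omission but do not correct the reported proportion.

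**Conclusion.** The concern holds. As written, SAP 8.1 is narrower than the period-based endpoint definitions and can remove qualifying subjects from the hepatic counts, always in the drug's favour. Among retained outputs, the most exposed are the two secondary endpoints in Table 14.3.2.1; the primary endpoint is less so.

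The frequency of omission cannot be derived from the documents, and none is claimed. One omitted subject is worth 2.0 percentage points at the planned maximum of 50. In the terminated study it is worth at most 16.7 points, on the inference that N is at least 6. This should be fixed. Confidence is medium, because the authors may have intended the rule only for by-visit displays and the safeguards may catch most cases.

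**What to change.** - In SAP 8.1, limit the exclusion of unscheduled results to by-visit summaries.
- In SAP 8.6.1 to 8.6.3, state that threshold counts use every liver result after first dose within Titration and Maintenance, scheduled or unscheduled. State also that local results count alongside central ones, each judged against its own laboratory's ULN. Local results are a separate choice, but Protocol 7.3.7.1 (Table 7) accepts local retests, so it should be made explicitly.
- State that HERC-adjudicated events count whichever visit detected them.
- Apply the same rules to retained Table 14.3.2.1.

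The cost is SAP wording and slightly more programming, on data already collected and listed. No protocol-defined endpoint or window changes. The hepatic counts may come out slightly less favourable.

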8.4.1 Medical History

A summary of medical history by medical history code (as per the case report form (CRF)) will be presented by system organ class (SOC) and preferred term (PT) using Medical Dictionary for Regulatory Affairs[®] (MedDRA) Version 23.0 or higher will be presented for the safety population.

A by subject listing including medical history will be presented for all subjects.

8.4.2 **Prior and Concomitant Medications**

Subject's CRF captured all medications within 1 month prior to study drug administration. However, additional medications specified in Exclusion Criteria 7, 8, and 9 in protocol Section 4.1.2 will also be recorded within the prior 3 months.

Prior medications are defined as medications where dosing ended prior to the first dose of study drug administration (exclusive). Concomitant medications are defined as medications that were taken between the first dose (inclusive) and last dose of study drug (inclusive). This also includes medications started prior and still ongoing at the start of the study drug. Details for imputing missing or partial start and/or stop dates of medication are described in section 7.2.1.

Separate summaries showing the number and percentage of subjects who took prior or concomitant medications will be presented by Anatomical Therapeutic Chemical (ATC) coding scheme of the World Health Organisation Drug Dictionary (WHO Drug) Global B3 March 2019 version or later on Level 2 term and preferred term for the Safety population.

A listing of prior/concomitant medications will be presented for all subjects. Prohibited medications/therapies if any will be highlighted by marking asterisk symbol (*) in the ATC column of the table and listing.

8.4.3 Concomitant Procedures

The Concomitant Procedures during the study will be coded using MedDRA Version 23.0 or higher. A by-subject listing including details of concomitant procedures will be presented for all subjects.

8.5 Treatment Exposure and Compliance

8.5.1 Study Treatment Exposure

Total dose and duration of exposure for study drug (section 7.1) for titration period (period of 6 weeks) and maintenance period (period of 52 weeks), will be summarized using descriptive statistics by titration and maintenance period based on safety population.

A by subject listing of exposure will be presented based for the safety population.

